4.2 Background

Neuromuscular blocking agents (NMBAs) are a class of medications routinely used during anesthesia to facilitate endotracheal intubation (1) and improve conditions for optimal surgery (2). However, these medications are also associated with respiratory complications in the early postoperative period due to residual neuromuscular blockade (RNMB) (3-5). Even when neuromuscular blockade is reversed in the operating room, postoperative residual weakness continues to be a common problem in the post-anesthesia care unit (PACU), and a significant number of patients continue to arrive in the PACU with objective evidence of residual neuromuscular blockade (6, 7). While not every patient with residual weakness develops a postoperative complication, many can develop avoidable critical respiratory events (8, 9). Furthermore, special populations such as the elderly are at particular risk for developing complications related to postoperative residual weakness (10). The use of quantitative monitoring has been demonstrated to reliably reduce the incidence of postoperative residual weakness and the ensuing complications (11-13).

Quantitative neuromuscular monitoring devices objectively measure residual weakness and display the results numerically. This is traditionally accomplished by performing a train-of-four (TOF) stimulation at the ulnar nerve and measuring the response of the adductor pollicis muscle. The degree of muscle weakness is determined by calculating the TOF ratio, which consists of the ratio of the fourth muscle contraction to the first. Adequate recovery that excludes clinically significant weakness from neuromuscular blockade is defined as a TOF ratio ≥ 0.9 , a measurement that can be determined reliably only with a quantitative monitor (14, 15). With an abundance of literature supporting the use of objective neuromuscular monitors, a panel of experts recently recommended the universal adoption of such devices whenever NMBA are utilized (16) however, quantitative monitors can be expensive and require additional training.

There are several types of quantitative neuromuscular monitors. These devices can be incorporated into the anesthesia workstation, allowing data to be seamlessly integrated into the electronic medical record. Unfortunately, this setup can preclude using these monitors in the PACU as portability is sacrificed. In contrast, other monitors exist as standalone, portable (handheld) units.

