
Many clinicians default to the antiquated practice of subjective monitoring (18, 19), which refers to visual or tactile evaluation of the train-of-four (TOF) in response to neurostimulation provided by peripheral nerve stimulation. However, subjective evaluation may provide inaccurate information and assessment of full recovery compared to objective evaluation (20, 21). A consensus statement by the international panel of experts in neuromuscular blockade issued in 2018 state that subjective evaluation is not predictive of adequate neuromuscular recovery, and is not sensitive to the presence of residual weakness. They state that their use should be abandoned

in favor of objective monitoring, because after the TOFR recovers to >0.40, anesthesia providers can no longer detect the presence of fade by subjective evaluation and they may assume a complete recovery from neuromuscular blockade, despite the presence of minimal levels of NMB(16). It is worth highlighting that after tracheal extubation, even minimal degrees of residual block is associated with impaired function of respiratory and pharyngeal muscles, upper airway obstruction (22),hypoxemia (23), and awareness during anesthesia (24)

Utilizing recommendations from the Good Clinical Practice (GCP) Guidelines for monitoring of neuromuscular function (25), we will compare acceleromyographic and electromyographic responses to train-of-four stimulation of the ulnar nerve in surgical settings where the arm movement is restricted by the surgical drapes (such as laparoscopic and robotic surgery). The time points of interest will include the onset of blockade following neuromuscular relaxant administration, maintenance of block, and reversal of blockade with sugammadex or neostigmine until adequate recovery (train-of-four ratio >0.9). The reliability of the two monitors will be evaluated post hoc by comparing the repeatability of responses, and the usability of the two monitors will be evaluated by the healthcare providers using the System Usability Scale (SUS) Plus scale, a simple, 10-item Likert scale with 5 response options for the evaluators (https://www.usabilitest.com/system-usability-scale).

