4.3 Risks and Benefits

- The benefits of using neuromuscular blockade monitoring devices:
 Early detection of optimal time for tracheal extubation; optimal management of intraoperative depth of neuromuscular block to facilitate surgical procedures; determination of appropriate time and dose of sugammadex reversal; and detection of residual neuromuscular blockade. This is currently the standard of care practice at Mayo Clinic.
- The risks of using neuromuscular blockade monitoring devices: Slight discomfort when electrical stimulation is administered in awake volunteers; however, our patients will be anesthetized, rendering this risk as extremely minor.

5 Study Objectives

Primary Objective

Compare the objective EMG-derived data using TetraGraph (TOFR, TOFC, PTC) with those obtained from the AMG-based TOFScan monitor and assess the reliability and usability of the two objective monitors.

Secondary Objective

Determine the incidence of failure to calibrate and monitor neuromuscular responses using the two monitors.

6 Study Design

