10.2 Statistical Methods

10.2.1 Descriptive Statistics

Analysis of agreement between the two monitors will be assessed using Bland-Altman. The limits of agreement are defined as bias \pm 2 SD, where SD denotes the standard deviations of the differences. Limits of agreement are interpreted as the reference range within which 95% of the differences will lie. The bias and the limits of agreements surrounding the bias (\pm 2 SD) will be calculated with 95% confidence intervals. Statistical significance will be defined as a p-value <0.05. Comparison of the usability of the two monitors will be made using the System Usability Scale (SUS) Plus. The SUS is particularly relevant to user experience when comparing two monitors that are based on different technologies (AMG and EMG). It will allow us to make a comparison of the two monitors in a surgical setting in which access to the monitoring muscle site (the thumb and hand) is limited. Because SUS is technology-neutral, we will be able to continue to use it in usability testing as technology evolves over the years, allowing us to continually evaluate and select the optimal monitoring technology available.

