18.2 Intraoperative Data

•		Date of Surgery (dd / mm / yyyy):		Examiner's Initials:		
Wrist circumference (right):		Wrist circumference (left):		Dominant side: L / R		
Ankle circumference (right):		Ankle circumference (left):				
Age (yrs):	Weight	(kg):		Height (cm):		BMI:
Muscle relaxant name	:					
Muscle relaxant total dose (mg):						
Time of first muscle re	elaxant	dose (mm :	: hh):		:	am / pm

Reversal agent name:					
Reversal agent dose (mg)	:				
Time of reversal agent administration (mm : hh):				:	am / pm
Time of extubation:		:		am / pm	

TetraGraph (TG) / TOFScan

	Time	TetraGraph (TG) Arm L/R	TOFScan Arm L / R	TOFR # 3 (if needed)
Calibrated baseline TOFR and supramax current				
TOFC=0 (post initial dose of NMBA)				
Time Interval (first recheck)				
Time Interval (second recheck)				
Time Interval				
Time Interval				
Time Interval				

Time Interval		
Time Interval		

Time Interval		
pre-SGX		
+60sec after SGX		
+120 sec after SGX		
+180 sec after SGX		
+260 sec after SGX		
Extubation		
Time to recovery following SGX (TOFR ≥0.9)		
T0 (on arrival to PACU)		
T5 (5 min after PACU arrival)		
T10 (10 min after PACU arrival)		

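### Section 10.2.1 sets one pair of Bland-Altman limits without saying which readings enter or checking that bias and spread are constant across the TOF range, and names no suitable agreement method for the counts

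*Combined protocol and SAP*

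**What the plan says.** The only agreement method is in section 10.2.1: "Analysis of agreement between the two monitors will be assessed using Bland-Altman". The limits are bias ± 2 SD, "where SD denotes the standard deviations of the differences", and they are read as follows: "Limits of agreement are interpreted as the reference range within which 95% of the differences will lie". The section does not name the variable or the readings that enter. It provides no check of constant bias or spread, no transformation, and no limits by level or stage of block.

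The material to be compared is broad. The primary objective in section 5 is to "Compare the objective EMG-derived data using TetraGraph (TOFR, TOFC, PTC) with those obtained from the AMG-based TOFScan monitor". Section 4.2 adds: "The time points of interest will include the onset of blockade following neuromuscular relaxant administration, maintenance of block, and reversal of blockade". The form in section 18.2 runs from a calibrated baseline, through a row for a TOF count of 0 after the first relaxant dose, to rows for extubation, a TOF ratio of at least 0.9, and arrival in the PACU.

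The upper end carries the clinical meaning. Section 4.2 says "Adequate recovery that excludes clinically significant weakness from neuromuscular blockade is defined as a TOF ratio" of at least 0.9. Section 10.1 gives one SD, 0.07, from a volunteer study of another AMG device, with no level of block stated.

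**The concern.** One bias and one SD give limits that hold 95% of differences at every level of block only if bias and spread are the same at every level. Section 4.2 defines the TOF ratio as the fourth contraction over the first, so it cannot fall below 0, and two readings near 0 have almost no room to differ. Constant spread therefore cannot hold over the full recorded range.

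At stake is how the published limits will be used. A reader will apply them at a particular level, most often near 0.9. If the limits are pooled over all levels, their stated coverage need not hold there, and the overall figure will not show it.

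TOFC and PTC raise a separate problem. Their differences are integers, and fractional ± 2 SD limits say little about how often the monitors agree exactly or differ by one or more steps.

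**Working it through.** **1. The plan's own figure.** For normal differences with constant bias and SD, coverage of bias ± 2 SD is Φ(2) − Φ(−2) = 95.45%. The stated 95% is reproduced under that condition.

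**2. Constant spread is impossible near 0.** Two non-negative readings with mean m cannot differ by more than 2m. With SD 0.07 (section 10.1) and no bias, the limits are ± 0.14. A difference of 0.14 needs m ≥ 0.07, so below that mean the limits lie beyond any possible difference. If readings at a TOF count of 0 on both monitors enter as a ratio of 0, each adds a difference of exactly 0 and shrinks the pooled SD. The plan does not say whether they enter.

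**3. Two levels of block (assumed).** Recovery SD is 0.07, a share w of readings is at recovery, and the deeper-block SD is 0.07/r, with no bias. Then pooled SD S = 0.07·√(w + (1−w)/r²), and coverage at recovery is 2Φ(2S/0.07) − 1. For w from 25% to 60%:

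| Recovery SD relative to deeper block | Coverage at recovery |
|---|---|
| 1.5 times | 87-92% |
| 2 times | 81-91% |
| 3 times | 75-89% |
| deeper-block differences all 0 | 68-88% |
| half (opposite pattern) | 99.7-100% (deeper block 86-93%) |

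Example: with w = 0.25 and all deeper differences 0, S = 0.07·√0.25 = 0.035, the limits are ± 0.070, and coverage is 2Φ(1) − 1 = 68%. Overall coverage in the rising-spread rows stays at 92-95%. A bias of 0.05 confined to recovery, with equal SDs, gives 94-96% at recovery, so bias alone matters little in this setting.

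**4. Three bands (assumed SDs for low, middle and recovery).** Pooled SD = √(Σ wᵢ·SDᵢ²); coverage in a band = 2Φ(2·pooled/SD of the band) − 1.

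- 0.03/0.06/0.10, equal shares: pooled 0.0695, recovery 83.6%.
- Same SDs, shares 50/30/20: pooled 0.0594, recovery 76.5%.
- 0.05/0.07/0.09, same two mixes: recovery 86-89%.
- 0.03/0.06/0.10 with recovery share 60% (the rest split equally): √0.0069 = 0.0831, recovery 90.3%. With 80%: √0.00845 = 0.0919, recovery 93.4%.
- 0.05/0.07/0.09 with recovery share 60%: recovery 92.3%. With 80%: √0.00722 = 0.0850, recovery 94.1%.
- Mid-range peak, 0.03/0.10/0.06, equal shares: pooled 0.0695, recovery 98.0%, middle 83.6%.
- Mid-range peak, shares 50/30/20: √0.00417 = 0.0646, recovery 96.9%, middle 80.3%.

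**5. Counts.** Let TOFC differ by ±1, symmetrically, in a share q of pairs. Then SD = √q and the limits are ± 2√q. For q < 25% the limits lie inside ±1 and coverage is exactly 1 − q: q = 10% gives ± 0.63 and 90%; q = 20% gives ± 0.89 and 80%. At q ≥ 25% coverage jumps to 100%. It equals 95% only at q = 5%.

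An uneven example has differences of 0 (80%), +1 (12%), −1 (5%) and +2 (3%). The mean is 0.12 − 0.05 + 0.06 = 0.13 and the variance 0.29 − 0.0169 = 0.2731. The SD is 0.523 and the limits are −0.92 to 1.18. Both −1 and +2 fall outside, so coverage is 92%.

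**6. Precision at the planned size.** The 95% interval half-width for one limit, with one difference per patient and SD 0.07, is t·0.07·√(1/n + 2/(n−1)): 0.024 at n = 105 and 0.042 at n = 35.

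**The case against.** A reader might infer that the limits will be too narrow at 0.9 and that the trial will overstate agreement there. The documents do not support that. They give no SD by level, and a bound at 0 explains small differences near 0 without showing that spread is largest at recovery. Section 9.2 has readings every 20 seconds after reversal, while the ratio may be changing quickly, so a mid-range peak is just as plausible; under it, recovery is over-covered. It would also be wrong to take comfort from assumed band SDs that happen to pool to 0.07. The figure in section 10.1 is a paired t-test input, not a pooled value over levels.

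Three further objections have force. First, pooling of all readings is inferred from a single definition and silence; the form records by stage, so analysis by stage is not ruled out. Second, read as a statement about all differences together, 95% stays roughly true. Third, section 10.2.1 does not expressly apply ± 2 SD to the counts; the gap is that nothing else is named for them.

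The stakes are also limited. The primary endpoint in section 6.4 is usability, the secondary endpoint in section 6.5 is failure frequency, and sections 8.3 and 10.2.2 call the study a pilot. Agreement is nevertheless part of the primary objective in section 5.

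These objections remove any firm claim about direction at recovery. They do not remove the unstated set of readings, the missing constancy check, the impossibility of constant spread down to 0, or the lack of a suitable method for the counts.

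**Conclusion.** The point holds in conditional form. If readings are pooled over the recorded range, a single pair of limits is too wide at very low ratios; this follows from the bound at 0. Whether it is too narrow elsewhere, and where, depends on an SD pattern that the documents do not give. Sections 3 and 4 of the working bracket it under assumed SDs and shares, with normal differences within each level: under-coverage at recovery if spread rises toward it, or under-coverage mid-range if spread peaks there. If bias and spread proved constant over the levels analysed, there would be no shortfall.

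For TOFC the failure of the 95% reading needs no assumption about level, because integer differences meet it only by coincidence. PTC, also a count, likewise has no suitable method named. The change is worth making before the data are analysed, and it does not touch the primary endpoint.

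**What to change.** Amend section 10.2.1 as follows.

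1. **TOF ratio.** State which paired readings enter, including how pairs with a TOF count of 0 are treated. Plot differences against means. Model bias and SD as functions of the mean, allowing for non-linearity (a straight line can miss a mid-range peak) and for repeated readings within a patient. Report the limits at a mean TOF ratio of 0.9 beside the pooled limits. Limits by stage of block, as recorded on the form, are an acceptable alternative. Do not define the recovery result only by a mean of 0.9 or more: readings of 0.95 and 0.80 average 0.875 and would drop out, although they disagree across the threshold.
2. **Counts.** For TOFC, report a 5 × 5 agreement table and weighted kappa. For PTC, do the same on grouped values, or report exact agreement and agreement within a pre-set number of counts. Give patient-level bootstrap intervals for both.

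The cost is a few sentences, a little more programming, and wider confidence intervals at a given level than for the pooled limits. The half-widths above (0.024 with 105 patients, 0.042 with 35) suggest that this is affordable. No new data are required.

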10.2.2 Handling of Missing Data

This is a prospective pilot study and therefore we do not anticipate any missing data. In the event of any unexpected missing data, no attempt to impute this missing data will be made; missing data will simply be treated as missing in the statistical analysis, and replacement participants will be enrolled to achieve the target accrual of n=35 participants.

10.3 Subject Population(s) for Analysis

Each participant who goes through the surgery and completes monitoring of residual neuromuscular blockade will be included in the primary analysis regardless of study withdrawal for any reason. In the event of any study withdrawals, in secondary analysis we will examine the sensitivity of our results to the exclusion of patients who withdraw.

11 Safety and Adverse Events

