however the setup is cumbersome and the lack of commercially available devices has relegated MMG to strictly research purposes. Acceleromyography (AMG) measures acceleration of a muscle group (typically the thumb) in response to stimulation (typically the ulnar nerve). This technique is similar to MMG, but instead of measuring the force of muscle contraction, an accelerometer fixed to the thumb measures the acceleration of the thumb in response to ulnar nerve stimulation. Based on Newton's Second law that states force is proportional to acceleration, the measured acceleration is correlated with the force of contraction in the clinical setting. There are currently two standalone AMG-based monitors available for clinical use: the STIMPOD (Xavant Technologies, Pretoria, South Africa) and the ToFscan (Draeger Medical Inc., Telford, PA). These devices represent improvements in AMG technology over its predecessor, the TOF-Watch (Schering-Plough Corp., Kenilworth, NJ, USA) as they utilize three dimensional transducers that can better quantify the complex motion of the thumb. Despite these advances, the use of AMG can be limited due to patient positioning that precludes free motion of the thumb, as well instances of awakening patients moving their thumb during measurements. Kinemyography (KMG) is based on similar principles to AMG, and relies on the thumb being able to move freely. Upon neurostimulation, KMG utilizes a piezoelectric motion sensor that is bent between the thumb and index fingers following muscle contraction. The degree of this bending is quantified and used to determine a TOF ratio. While Datex-Ohmeda (Helsinki, Finland) manufactures a KMG device that can be incorporated into the anesthesia work station, there are no currently available standalone KMG devices. Electromyography (EMG) devices measure electrical activity, termed compound muscle action potentials (cMAPs) following nerve stimulation (typically at the adductor pollicis muscle after ulnar nerve stimulation). As EMG measures cMAPs and does not require freely moving thumbs for accurate measurements, many experts have referred to this monitoring modality as the "new gold standard". TetraGraph (Senzime AB, Uppsala, Sweden) is a standalone EMG-based device that is FDA-approved. We have previously investigated this device and presented our findings at several annual meetings such as International Anesthesia Research Society (May 2018, May 2017, May 2013), the Society for Technology in Anesthesia (January 2018), and the American Society of Anesthesiologists (October 2017, October 2012), European Society of Anaesthesiology (June 2018, June 2015) (17). Furthermore, we have recently submitted abstracts to the PostGraduate Assembly in Anesthesiology in December 2018 as well as a manuscript describing a multicenter, volunteer study investigating TetraGraph versus AMG-based monitors. Our work thus far has found this device to be easy to apply, reliable, and able to provide comparable measurements to other quantitative monitors.

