6.4 Primary Study Endpoints

The primary endpoint of the study will be to determine the usability of the two monitors using the SUS Plus scale.

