6.5 Secondary Study Endpoints

The secondary endpoint is to determine the reliability of the two monitors, by comparing the frequency of each monitor's failure to calibrate and measure evoked responses.

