18.4 TOFScan SUS

Question			R	ating			
I think that I would like to use TOFScan		1	2	3	4	5	
frequently.	Strongly Disagree	0	0	0	0	0	Strongly Agree
		1	2	3	4	5	
I found TOFScan unnecessarily complex.	Strongly Disagree	0	0	0	0	0	Strongly Agree
I d. Torg		1	2	3	4	5	
I thought TOFScan was easy to use.	Strongly Disagree	0	0	0	0	0	Strongly Agree
I think that I would need the support of a		1	2	3	4	5	
technical person to be able to use TOFScan.	Strongly Disagree	0	0	0	0	0	Strongly Agree
I found the various functions in TOFScan were		1	2	3	4	5	
well integrated.	Strongly Disagree	0	0	0	0	0	Strongly Agree
I thought there was too much inconsistency in		1	2	3	4	5	
TOFScan.	Strongly Disagree	0	0	0	0	0	Strongly Agree
I would imagine that most people would learn		1	2	3	4	5	
to use TOFScan very quickly.	Strongly Disagree	0	0	0	0	0	Strongly Agree
		1	2	3	4	5	
I found TOFScan very cumbersome to use.	Strongly Disagree	0	0	0	0	0	Strongly Agree
		1	2	3	4	5	
I felt very confident using TOFScan.	Strongly Disagree	0	0	0	0	0	Strongly Agree
I needed to learn a lot of things before I could get going with TOFScan.		1	2	3	4	5	

Strongly Disagree OOOOO Strongly Agree

19 List of In-Text Figures

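### Section 10.3 ties the primary analysis to completed monitoring and 10.2.2 replaces for missing data without exempting device failure, so on one open reading failed cases can leave the usability comparison

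*Combined protocol and SAP*

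**What the plan says.** - **Analysis set (10.3).** "Each participant who goes through the surgery and completes monitoring of residual neuromuscular blockade will be included in the primary analysis". The one qualification is "regardless of study withdrawal for any reason". The one sensitivity analysis takes withdrawn patients out; none brings back patients who did not complete monitoring. No other section defines an analysis set.
- **Primary endpoint (6.4).** The aim is to "determine the usability of the two monitors using the SUS Plus scale". Section 10.3 does not name SUS. The primary objective in section 5 also compares TOF ratio, TOF count and post-tetanic count between the monitors, and 10.1 sizes the study on TOF ratio.
- **Missing data (10.2.2).** None is anticipated. If some occurs unexpectedly it is not imputed: "missing data will simply be treated as missing in the statistical analysis, and replacement participants will be enrolled", up to a target of 35, which is the per-centre number in 10.1.
- **Secondary endpoint (6.5).** Reliability is judged by how often each monitor shows "failure to calibrate and measure evoked responses". The secondary objective in section 5 is similar: "Determine the incidence of failure to calibrate and monitor neuromuscular responses using the two monitors".
- **Design.** Every patient has both monitors (8.2), the study is open-label (8.3), and the provider rates both monitors at the end of each case (4.1).

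**The concern.** Failure of a monitor is an outcome of this study, yet it can also prevent a patient from completing monitoring, and it leaves gaps in the TOF readings. A completion condition combined with replacement can therefore select the analysed patients on an outcome.

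The protocol gives reason to expect failures to be unequal. Section 4.2 says that "the use of AMG can be limited due to patient positioning that precludes free motion of the thumb", and restricted arms are the setting studied. Section 8.1 says that the EMG signal can still be measured when the thumb cannot move.

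Failure could plausibly lower the rating. The SUS form asks the provider to respond to "I felt very confident using TOFScan", and other items ask about inconsistency and cumbersomeness. If failed cases leave the SUS comparison, the cases most informative about usability in this setting leave with them, and the monitor that fails more is flattered. In an open-label study the reading of the rule should be fixed before the data are seen.

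**Working it through.** **Does the text settle who is analysed?**

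1. Section 10.3 requires completion of monitoring but does not say whether one working monitor is enough, although 8.2 puts two on every patient.
2. Its exception covers withdrawal. A device failure is not a withdrawal.
3. Section 10.2.2 anticipates no missing data, while 6.5 counts failures to measure. It does not say whether a reading lost to failure is missing data in its sense, or whether it triggers replacement.
4. Section 4.1 asks for both ratings after each case without requiring that monitoring succeeded. A SUS rating can therefore exist for a failed case.

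Two readings remain open. Strict: completion needs both monitors. Lenient: one is enough.

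**How far apart are the readings?** The documents give no failure rate and no SUS figure, so there is no plan figure to reproduce here. All rates below are assumptions.

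Let fT and fE be the failure rates of TOFScan and TetraGraph, d the rating penalty for a failure (the same for either monitor), and D the TetraGraph-minus-TOFScan SUS difference when neither fails.

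- All attempted cases: D + d(fT − fE).
- Strict reading (any failed case left out): D. The shift is d(fT − fE), toward the monitor that fails more.
- Lenient reading (left out only if both fail, failures independent): D + d(fT − fE)/(1 − fT·fE). The shift is small and has the opposite sign.

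| fT / fE | Strict shift | Strict, d = 20 | Lenient shift | Lenient, d = 20 |
|---|---|---|---|---|
| 10% / 5% | 0.05d | 1 point | 0.05/0.995 − 0.05 = 0.0003d | 0.005 |
| 20% / 5% | 0.15d | 3 points | 0.15/0.99 − 0.15 = 0.0015d | 0.03 |
| 30% / 5% | 0.25d | 5 points | 0.25/0.985 − 0.25 = 0.0038d | 0.08 |

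Replacement does not undo the strict shift. Replacements face the same condition, so only patients in whom both monitors worked are counted, however many are enrolled.

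**What would not replacing failures cost in TOF-ratio pairs?** The total in 10.1 reproduces as 3 × 35 = 105. If every failure lost all of a patient's pairs and failures were independent, the pairs kept would be 105 × (1 − fT)(1 − fE):

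- 20% / 5%: 105 × 0.80 × 0.95 = 79.8, about 80.
- 30% / 5%: 105 × 0.70 × 0.95 = 69.8, about 70.

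The corresponding averages per centre are 35 × 0.76 = 26.6 and 35 × 0.665 = 23.3. Section 10.1 names 23 patients for 90% power. That number cannot be reproduced from the stated inputs because the target difference is not given; with SD 0.07 and two-sided 0.05, an assumed difference of 0.05 returns 23. It serves here only as a yardstick.

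**The case against.** The strongest reply is that nothing in the plan orders failed cases to be removed.

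- **Section 10.3 may not be about SUS.** The objective in section 5 and the sample size in 10.1 concern TOF data. For an agreement analysis, requiring completed monitoring is sensible. This stands as an ambiguity. But 6.4 names SUS as the primary endpoint, and if the condition was meant only for TOF pairs, 10.3 does not say so.
- **Section 10.2.2 covers unexpected gaps and treats them as missing.** Failure is a named endpoint, so it is arguably not unexpected, and treating data as missing suggests that the patient is kept with whatever data exist. This stands in part. The section also says that no missing data are anticipated, so it does not settle how a failure is classed.
- **The lenient reading is at least as natural.** The condition is worded for the patient, not for each monitor. This stands, and on that reading nothing of substance is lost.
- **Failures will be visible.** Section 12.3 requires missing data to be explained, and the 18.2 sheet has a column per monitor and a baseline calibration row. This helps in identifying failures, but it does not say who enters which analysis.

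A reader might infer that the plan deletes failed cases, or that the failure endpoint itself is restricted to completers. The documents support neither. Section 10.3 says who is included and speaks only of the primary analysis, 10.2.2 does not say that the original patient's ratings are dropped, and 4.1 requests ratings in every case.

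**Conclusion.** The point holds as a gap in the rules that permits selection on an outcome; it is not a stated instruction to select. The completion condition in 10.3 and the unqualified replacement rule in 10.2.2 can together remove failed cases from the SUS comparison if completion means that both monitors worked.

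The true size is unknown. Under the assumed rates and an assumed 20-point penalty, the strict reading shifts the SUS contrast by 1 to 5 points toward the monitor that fails more, and the lenient reading by less than 0.1 point. The strict figures rest on a failure lowering that monitor's rating, by the same amount for either monitor; the lenient figures also assume independent failures. That TOFScan is the one favoured is an expectation drawn from 4.2 and 8.1, not a result. The text should be fixed, with medium confidence that the gap would matter in practice.

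**What to change.** 1. **Section 10.3.** Analyse SUS and device failure in all patients in whom placement of both monitors was attempted, whether or not monitoring was completed, using the end-of-case ratings already requested in 4.1. Restrict to complete TOF-ratio pairs only for the Bland-Altman and paired TOF-ratio analyses.
2. **Section 10.2.2.** State that failure to calibrate or to measure is an outcome, not missing data and not grounds for replacement. Patients added to obtain more TOF pairs are additional; the earlier patients stay in the SUS and failure analyses.

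This changes text in two subsections and needs no new procedure. The downside is fewer TOF-ratio pairs if no patients are added: about 80 of 105 at the assumed 20%/5% and about 70 at 30%/5%. Both pooled counts exceed the 23 in 10.1. If 23 was meant for each centre, a centre could fall short, since the average at 30%/5% is only 23.3; adding patients under item 2 would deal with that.

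A per-patient definition of failure, a named test for comparing failures, and a check that the case report form records failure for each monitor would be useful clarifications, but this point does not depend on them.
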